### **5.2.2 Impact of COVID-19 on Study Visits**

A listing of visits impacted by COVID-19 will be presented for all participants based on the ASP. This will include visit, visit date, study day, impact category, relationship to COVID-19 and the narrative of the event. Participants who discontinue treatment or stop study participation due to COVID-19 pandemic will be included in participant disposition summaries.

The number and percentage of participants with visits impacted by COVID-19 for any reason will be summarized by planned treatment sequence and impact category (overall and for each category separately). The denominator for the percentages will be the number of participants in the RS.

## **5.3 Demographics and Other Baseline Characteristics**

### **5.3.1 Demographics**

All demographic characteristics will be summarized for the FAS and RS by treatment sequence and overall. The following continuous variables will be summarized using descriptive statistics:

- Age at Screening (years)
- Weight (kg)
- Height (cm)
- BMI (kg/m^2)

Body mass index in kg/m^2 will be calculated based on the height (in m) and the weight (in kg) using the following formula:

$$\text{BMI (kg/m}^2\text{)} = \text{weight (kg)}/[\text{height (m)}]^2$$

The following categorical variables will be summarized using frequency counts and percentages:

- Age (18-<65, 65-<85, ≥85 years) based on requirements for European Union Drug Regulating Authorities Clinical Trials (EudraCT) reporting
- Age (≤18, 19-<65, ≥65 years) based on requirements for clinicaltrials.gov reporting
- Weight (<100kg, >=100kg)
- BMI (<30 kg/m^2 and ≥30 kg/m^2)
- Gender
- Race
- Ethnicity
- Country

A listing of demographics by study participant and planned treatment sequence will be presented for the ASP. This will include participant ID, the year of birth, country, age at Screening (in years), gender, race, ethnicity, height (cm), weight (kg) and body mass index (BMI) at Screening.

### **5.3.2 Other Baseline Characteristics**

Descriptive statistics of BPI-SF Interference, Fatigue and Pain NRS and FIQR Baseline scores will be summarized by planned treatment sequence. Additionally, time (year) since diagnosis and time (year) since first symptoms of FMS based on the Screening date will be summarized in years using the SS-r (see Appendix 2 [Section 8.2.4](#) for details on how to handle partial dates). Time since diagnosis and time since first symptoms of FMS will also be listed.

### **5.3.3 Medical History**

Medical history and ongoing medical conditions will be listed for the RS and summarized for the SS-r by planned treatment sequence and overall, MedDRA system organ class (SOC) and preferred term (PT). The reported term will be included in the listing. The summary will include the number and percentage of study participants and will be sorted alphabetically by SOC, High Level Group Term (HLGT) and, within HLTG, by descending incidence of PT, based on the 'All Participants' column. Family medical history collected for PDILI events will be listed.

### **5.3.4 History of Headache**

A listing of the history of headache responses will be presented by planned treatment sequence for the SS-r.

### **5.3.5 Medical History on Pain Management Programs**

A by participant listing of the information collected on the medical history of pain management programs electronic case report form (eCRF) will be presented by planned treatment sequence for the SS-r.

### **5.3.6 Prior and Concomitant Medications**

Prior and concomitant medications will be classified in the below categories. Past medications are a subset of prior medications.

**Prior medications** include medications that started prior to the first dose of IMP in Run-In. This includes Pre-Screening medications which are received prior to the date of Screening and includes any medications that started prior to dosing in Run-In and continued after the first dose in Run-In (prior and concomitant).

**Concomitant medications** include any medications that have been taken at least once on or after the date of first administration of IMP in Run-In. Permitted concomitant medications are limited to those listed in [Section 6.5.1](#) of the protocol.

Based on the above definitions a medication may be considered as both prior and concomitant.

Prior and concomitant medications will be listed for the SS-r by planned treatment sequence and will include WHO-DD Anatomical Main Group [Level 1 term text], Pharmacological Subgroup [Level 3 term text], PT and reported term where applicable. All periods for which medication was received will be included in the listing. Periods are assigned based on whether a participant entered the given period. Full details of the rules for period assignment are described in [Appendix 4 Section 8.4.2](#)

Prior medications will be summarized by planned treatment sequence for the SS-r and will include WHO-DD Anatomical Main Group [Level 1 term text], Pharmacological Subgroup [Level 3 term text] and PT. This table will include all medications that started and stopped prior to the first dose of IMP in Run-In and medications that started prior to and continued after the first dose of IMP in Run-In.

Concomitant medications will be summarized by treatment group and period for the SS-r and will also include WHO-DD Anatomical Main Group [Level 1 term text], Pharmacological Subgroup [Level 3 term text] and PT.

### **5.3.7 Prior and Concomitant Medical Procedures**

Prior and concomitant medical procedures will be classified in the below categories.

**Prior medical procedures** are defined as procedures occurring prior to the date of informed consent.

**Concomitant medical procedures** are defined as procedures occurring on or after the date of informed consent.

Prior and concomitant medical procedures will be listed only. The listing will contain the date of procedure and the period of onset. For the purpose of assigning the medical procedure to a category and to define the period of onset, partial and missing start dates will be imputed based on the rules defined in [Appendix 2 Section 8.2.3](#). Medical procedures will be assigned to a period based on the date of the procedure.

### **5.4 Measurements of Treatment Compliance**

As dosing is performed in-house by the investigator or member of staff, no specific assessment of compliance is warranted. Any dosing deviation will be addressed in the DEM and described in the CSR.

## **5.5 Pharmacokinetics and Pharmacodynamics**

### **5.5.1 Pharmacokinetics**

All pharmacokinetic summaries will be presented using the PKS and listings will be presented based on the SS-r. PK samples from study participants on placebo will not be analyzed. Consequently, participants randomized to Sequence 3 will be excluded from the analyses described in this section and will not be included in TFLs. PK samples taken prior to the intended dose will be associated with the relevant dose for the purpose of tables and analyses. Samples taken after intended dose will be excluded from the analysis.

The listing of plasma concentrations will include treatment sequence, visit, actual blood sampling time (presented as time relative to the start time of dosing of the respective visit), scheduled sampling time, and days since the previous dose.

The plasma concentrations of rozanolixizumab at each scheduled assessment will be summarized by treatment group and period using descriptive statistics and presented in the form of table and figures. In addition, individual plasma concentrations will be shown in a figure by participant and actual time since the time of first active dose.

The following rules will apply for PK data listings and summaries:

- Values below the LLOQ will be reported as BLQ.
- Descriptive statistics of concentrations will be calculated if at least 2/3 of the concentrations are quantified at the respective time point.
- Values that are BLQ will be replaced by the numerical value of the LLOQ/2 (0.1ug/mL).
- The 95% CI lower and 95% CI upper will be left blank if the SD (or equivalently, the geoCV) is 0
- The geometric coefficient of variation (CV) is calculated as  $\sqrt{(\exp(\text{std ln}^2)-1)}*100$ , where std ln is the standard deviation of the log-transformed data.

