Certain clinical laboratory results have the potential to unblind the investigator, site personnel, and study team. These results will not be reported to investigative sites or other blinded personnel (see Section 10.2 for a list of these clinical laboratory parameters). A medical monitor independent from the study team and unblinded to the serum IgG and albumin levels, but blinded to actual treatment assignment (an independent unblinded medical monitor) will monitor these parameters during the Treatment Period. If temporary treatment discontinuation due to low serum IgG levels or low serum albumin levels (as per Section 7.1.4) is required, the independent

unblinded medical monitor will contact the IRT system to initiate mock infusions with only placebo. This procedure will take place irrespective of the randomized IMP. Allocation of mock kit numbers will be handled via the IRT. The independent unblinded medical monitor will re-initiate the IMP via the IRT system when the serum IgG and/or albumin levels have returned to protocol-defined thresholds specified in Section 7.1.4.

Further details of maintenance of the study treatment blind are provided in the IMP Handling Manual and Site Unblinded Team Management Plan.

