9.4.2 Other analyses

9.4.2.1 PK analyses

Plasma concentration data of rozanolixizumab will be summarized by treatment group, actual dose received, and time point using the number of available observations, mean, median, SD, minimum, maximum, geometric mean (and associated 95% confidence intervals), and geoCV (assuming log-normally distributed data). Values below the LLOQ will be reported with a clear sign indicating that they were below the LLOQ. Descriptive statistics of concentrations will be calculated if at least two-thirds of the individual data points are quantifiable (\geq LLOQ). However, minimum and maximum will always be reported even if $<2/3$ are quantifiable; minimum should be reported as value of LLOQ where it is not above this value.

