9.4.2.3 PD analyses

For all PD variables, descriptive statistics for the value, change from Baseline, and/or percentage change from Baseline will be tabulated by treatment group, actual dose received, and time point. The PD variables will include serum total IgG and IgG subclass concentrations.

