### **5.5.2 Pharmacodynamics**

Venous blood samples will be collected for measurement of total serum IgG and subclass IgG concentrations as PD assessments. The observed concentration, change and percent change from Baseline in total serum IgG and IgG subclasses will be listed. The listings will also report the maximum change and maximum percent change from Baseline in each Treatment Period, based on the maximum decrease or smallest increase if no decrease is observed.

The observed concentration, change and percent change from Baseline, and maximum change and percent change, in total serum IgG and IgG subclasses will be summarized for each planned treatment sequence on the PDS.

The observed concentration, change and percent change from Baseline in total serum IgG and IgG subclasses will be summarized by each assessment for each treatment group on the PDS. There will be three treatment groups: placebo, rozanolixizumab for up to 12 weeks [Sequence 1, Period 1 and Sequence 2, Period 2], or rozanolixizumab given beyond 12 weeks [Sequence 1, Period 2].

The observed concentration and percent change from Baseline in Total IgG will be summarized by each visit by planned treatment sequence and Baseline body weight categories (<100kg, and >=100kg).

The observed Baseline Total IgG, and the maximum percent change from Baseline for each Treatment Period will be summarized by planned treatment sequence and the Baseline body weight categories (<100kg, and >=100kg).

For the purpose of calculating change from baseline or for descriptive statistics, BLQ values will be imputed with half of the lower limit of quantification (LLOQ).

Median percent change from Baseline values in Total IgG will be plotted against study week for the entire study duration, by planned treatment sequence.

Median percent change from Baseline values in Total IgG will be plotted against assessment number (1-4 within the given treatment period), by treatment group.

Median percent change from Baseline in total IgG will be plotted against study week for the entire study duration, by planned treatment sequence and Baseline body weight categories (<100kg, and >=100kg).

Spaghetti plots will be provided for Total IgG and percent change from Baseline in Total IgG over time stratified by treatment sequence.

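### The SAP drops the protocol's split of PK and IgG summaries by actual dose received without listing the change, so scheduled troughs after mock, held or stopped doses are pooled with 560 mg weekly troughs (minor).

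*SAP*

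**What the plan says.** For PK, protocol 9.4.2.1 states: "Plasma concentration data of rozanolixizumab will be summarized by treatment group, actual dose received, and time point". For IgG, protocol 9.4.2.3 states that the descriptive statistics "will be tabulated by treatment group, actual dose received, and time point".

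The SAP sets its own grouping in both places. For PK (5.5.1): "The plasma concentrations of rozanolixizumab at each scheduled assessment will be summarized by treatment group and period using descriptive statistics". For IgG (5.5.2), one summary is by sequence ("in total serum IgG and IgG subclasses will be summarized for each planned treatment sequence on the PDS") and another by treatment group ("in total serum IgG and IgG subclasses will be summarized by each assessment for each treatment group on the PDS"). Neither section mentions dose received.

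SAP 5.1.2 lists three departures from the protocol: the Baseline definition, the move from 10 to 12 weeks for the pain and fatigue scores, and the placebo-based imputation that will not be produced. The PK and IgG grouping is not among them.

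Protocol 6.3.1.1 describes what happens when dosing is paused for low IgG or albumin: the "unblinded medical monitor will contact the IRT system to initiate mock infusions with only placebo". Protocol 7.1.4 allows no make-up dose after a pause, and protocol 7.1.3 asks that participants who stop treatment permanently stay in the study where safe and feasible.

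**The concern.** Protocol 6.6 does not permit dose modification, so the planned dose in a rozanolixizumab period is always 560 mg. The dropped factor therefore matters mainly where a participant in such a period receives no active drug. The protocol creates three such situations: mock infusions, other temporary holds, and permanent discontinuation with continued visits.

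If these samples are not separated, the rozanolixizumab rows mix troughs one week after 560 mg with troughs after a longer gap. Protocol 4.3 justifies the dose by the exposure it should reach and by an IgG reduction of about 70%. The trough and IgG tables are where a reader would check both, and they would describe a mixture without saying so.

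**Working it through.** **1. The texts side by side**

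| Item | Protocol | SAP |
|---|---|---|
| PK | treatment group, actual dose, time point (9.4.2.1) | treatment group and period at each assessment (5.5.1) |
| IgG | treatment group, actual dose, time point (9.4.2.3) | planned sequence; treatment group by assessment (5.5.2) |
| Change declared | n/a | not in 5.1.2 |

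SAP 1 falls back on the protocol only where the SAP does not specify. Sections 5.5.1 and 5.5.2 do specify, so the fallback does not restore the protocol grouping.

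**2. Where an off-drug sample lands**

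- SAP Table 5-3 defines treatment groups by sequence and period, not by doses received.
- SAP 5.1.1.2 allocates PK and PD measurements to a period by visit.
- SAP 5.5.1 excludes only samples taken after the intended dose. It also says that samples from participants on placebo are not analysed, but draws from this only the exclusion of Sequence 3.
- The exclusion of data after discontinuation (SAP 5.8.2.1) belongs to the efficacy estimand.

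So a scheduled trough after a mock, held or stopped dose counts as rozanolixizumab data by default.

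**3. Size for PK (illustration only)**

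From the documents: 20 participants per sequence; a below-quantification value is set to 0.1 ug/mL (SAP 5.5.1). Assumed: the on-drug geometric mean G, that the off-drug sample is below quantification, and the number k of such samples among n = 20.

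Ratio of reported to on-drug geometric mean = (0.1/G)^(k/n).

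| G (ug/mL) | k = 1 | fall | reported geoCV, k = 1 |
|---|---|---|---|
| 2 | 0.861 | 14% | 99% |
| 10 | 0.794 | 21% | 163% |
| 20 | 0.767 | 23% | 204% |
| 50 | 0.733 | 27% | 278% |

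With k = 2 the ratio runs from 0.741 (G = 2) to 0.537 (G = 50), a fall of 26% to 46%.

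The geoCV column assumes 19 on-drug values with a log-scale SD of 0.5, that is sqrt(exp(0.25) − 1) = 53%. Adding one value of 0.1 gives a log variance of [18 × 0.25 + (19/20) × ln(0.1/G)²]/19. For G = 2 this is (4.5 + 0.95 × 8.974)/19 = 0.686, and sqrt(exp(0.686) − 1) = 99%.

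The rule that two-thirds of values must be quantifiable does not intervene: 19/20 = 95% and 18/20 = 90%.

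**4. Direction for IgG**

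Reduction = 1 − level/baseline. A hold for low IgG starts below 1.09 g/L and may end at 2 g/L or more (protocol 7.1.4). Screening IgG must exceed 5.5 g/L (exclusion 30a).

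| Baseline (g/L) | at 1.09 g/L | at 2 g/L |
|---|---|---|
| 5.6 | 80.5% | 64.3% |
| 10 | 89.1% | 80.0% |

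At 2 g/L the reduction is still at least 70% for any baseline of 2/0.30 = 6.67 g/L or more. These participants sit near or beyond the target.

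Permanent stops act the other way. Take 15 participants (20 less 25% dropout) with an on-drug reduction of 70%, three of whom have stopped and show a reduction r. The mean is (12 × 70 + 3r)/15: 56% for r = 0, 60% for r = 20 and 64% for r = 40. Both the count and r are assumptions.

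**The case against.** The strongest objections concern consequence and remedy.

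- **IgG.** A reader might infer that pooling understates both the trough and the IgG reduction. The documents do not support this for IgG-triggered holds, as step 4 shows. Taking those samples out of the main IgG table would also remove participants because their IgG fell very low. That is selection on the outcome, and it would tend to lower the apparent reduction. This objection stands and shapes the fix.
- **Blame on under-dosing.** A reader might also infer that a null efficacy result could be put down to under-dosing. That is speculation. The PK listing shows days since the previous dose, individual concentrations and IgG courses are plotted, and infusions excluding mock ones are tabulated (SAP 5.5.1, 5.5.2, 5.6.1). The cause of a low trough could be traced, although the summary tables would stay mixed.
- **Size.** Nothing in the documents says that a trough after one missed dose is below quantification, or how often it happens. The median is reported too and would barely move with one such value in 20; the IgG time-course figures use medians.
- **Permanent stops.** Protocol 7.1.3 gives priority to the EOT/EW and SFU/EOS visits, where no PK sample is scheduled, and SAP 5.1.5 does not re-map PK from the EW visit. Off-drug troughs after a permanent stop arise only at PK visits that are still attended. For IgG the route is wider, since in-window EW samples are re-mapped.
- **Existing exclusions.** Important deviations can remove participants from the PDS or from PK analyses, which may catch some missed doses. A mock infusion directed by the protocol is not a deviation. SAP 5.8.3 counts mock infusions as missed doses within a population drawn from the FAS, so it treats recipients as remaining in the FAS. The PKS is drawn from the SS-r in any case.
- **Unseen documents.** The table shells could carry the split, and the protocol does not define the term. Reading it as 560 mg versus no active drug is an inference from protocol 6.6. The SAP text as it stands still differs from the protocol.

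**Conclusion.** The discrepancy is established from the text: both protocol sections call for the actual-dose grouping, both SAP sections replace it, and SAP 5.1.2 is silent. For PK the consequence follows by default: off-drug troughs at scheduled visits are pooled with on-drug ones, which lowers the reported trough and inflates geoCV.

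The 14% to 27% fall for one value in 20 is an illustration. It rests on an assumed on-drug trough of 2 to 50 ug/mL, on the off-drug sample being below quantification, and on the assumed count. For IgG no single direction can be claimed: permanent stops and holds not triggered by IgG would dilute the mean reduction, but IgG-triggered mock recipients need not.

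Severity is minor. PK and IgG are exploratory endpoints summarised descriptively, and SAP 2 plans no formal hypothesis testing.

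**What to change.** - **SAP 5.5.1:** restore the protocol grouping by treatment group, actual dose received and time point. Show troughs whose preceding scheduled infusion was mock or missed, or which follow permanent discontinuation, in a separate 'dose not received' row.
- **SAP 5.5.2:** keep the all-samples IgG summary as the main table, to avoid selecting on the outcome, and add the split by actual dose received alongside it.
- **Otherwise:** if the sponsor prefers the present grouping, list the change in SAP 5.1.2 and justify it.

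The cost is one derived flag, built from dosing records that SAP 5.6.1 already lists, and slightly fewer samples in the on-dose PK rows. It also brings PK and IgG into line with the SAP's own practice, since mock infusions are already separated for exposure (5.6.1) and counted as missed in the efficacy sensitivity analysis (5.8.3).

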### **5.5.2 Pharmacodynamics**

Venous blood samples will be collected for measurement of total serum IgG and subclass IgG concentrations as PD assessments. The observed concentration, change and percent change from Baseline in total serum IgG and IgG subclasses will be listed. The listings will also report the maximum change and maximum percent change from Baseline in each Treatment Period, based on the maximum decrease or smallest increase if no decrease is observed.

The observed concentration, change and percent change from Baseline, and maximum change and percent change, in total serum IgG and IgG subclasses will be summarized for each planned treatment sequence on the PDS.

The observed concentration, change and percent change from Baseline in total serum IgG and IgG subclasses will be summarized by each assessment for each treatment group on the PDS. There will be three treatment groups: placebo, rozanolixizumab for up to 12 weeks [Sequence 1, Period 1 and Sequence 2, Period 2], or rozanolixizumab given beyond 12 weeks [Sequence 1, Period 2].

The observed concentration and percent change from Baseline in Total IgG will be summarized by each visit by planned treatment sequence and Baseline body weight categories (<100kg, and >=100kg).

The observed Baseline Total IgG, and the maximum percent change from Baseline for each Treatment Period will be summarized by planned treatment sequence and the Baseline body weight categories (<100kg, and >=100kg).

For the purpose of calculating change from baseline or for descriptive statistics, BLQ values will be imputed with half of the lower limit of quantification (LLOQ).

Median percent change from Baseline values in Total IgG will be plotted against study week for the entire study duration, by planned treatment sequence.

Median percent change from Baseline values in Total IgG will be plotted against assessment number (1-4 within the given treatment period), by treatment group.

Median percent change from Baseline in total IgG will be plotted against study week for the entire study duration, by planned treatment sequence and Baseline body weight categories (<100kg, and >=100kg).

Spaghetti plots will be provided for Total IgG and percent change from Baseline in Total IgG over time stratified by treatment sequence.

For correlation analysis between clinical endpoints and PD data, scatterplots including regression lines and Pearson correlation coefficients will be provided for change and percent change from Baseline at Visit 15 (or Visit 27) in total IgG versus:

- Change from Baseline at Visit 15 and Visit 27 in BPI-SF interference.
- Change from Baseline at Visit 13 and Visit 25 for FIQR
- Change from Baseline based on the average score at Visit 14 and Visit 26 and the following 6 days, for pain NRS and fatigue NRS.

Scatterplots will be summarized by treatment group.

Boxplots of maximum change and percent change from Baseline for Total IgG will also be plotted by sequence and period, for a total of 6 box plots.

All pharmacodynamic summaries and figures will be presented based on the PDS, and listings will be presented using the SS-r.

